5.6.4. Percent Predicted SVC

General Description

Vital capacity will be measured by means of the slow vital capacity (SVC) test using a facemask with the participant sitting upright. SVC will be determined by performing at least 3 trials. If the difference between the two highest values of the three trials is $\geq 10\%$, then up to 5 trials may be performed. The highest percent predicted SVC value at each visit will be used for the analysis.

Descriptive Statistics

Descriptive statistics, including observed value and change from baseline in the percent predicted SVC, will be evaluated by visit with descriptive statistics (mean, SD, median, 1st and 3rd quartiles, range) for pooled group DL and Part 2 BIIB105 60 mg in the FAS population.

Spaghetti plots will be presented by treatment group.

Statistical Analysis

The following analyses will be performed for pooled group DL in the FAS population.

For integrated analyses of Part 1 and Part 2 for Cohorts D1 and D2, difference between treatment groups (i.e. Early-start BIIB105 120 mg and Placebo/Delayed-start BIIB105 120 mg) in least square means of Week 40 change from baseline with corresponding standard errors and 95% confidence intervals taken from the ANCOVA described in Section [5.6.1](#) based on the multiple imputation dataset.

5.6.5. Time to Event Analyses

Time-to-event endpoints include

- Time to death or permanent ventilation (≥ 22 hours of mechanical ventilation [invasive or noninvasive] per day for ≥ 21 consecutive days)
- Time to death

CONFIDENTIAL

The information contained herein may not be used, disclosed, or published without the written consent of Biogen MA Inc.

- Time to death, permanent ventilation (≥ 22 hours of mechanical ventilation [invasive or noninvasive] per day for ≥ 21 consecutive days), or withdrawal from study due to disease progression.

Time to event endpoints will be summarized using Kaplan-Meier curves based on randomization in Study 275AS101 Part 1.

Participants without an event will be censored at the last known alive dates, defined as the interim cut date for 275AS101 (March 12, 2024) or as the last date in the database with any actual study visit or measurements indicating their alive status.

Summary of time-to-event data will be presented by treatment group including number of participants with the event (separate by each individual event for composite event) and number of participants who were censored. Kaplan-Meier plots will be presented. The median survival time, percentiles (5th, 10th, 25th, 75th) and associated 95% confidence limits, and proportion of participants with an event at a list of time points (Week 26, 52, 78, etc.) will be estimated using the Kaplan-Meier. Treatment comparison for time to event will be based on a log rank test. A Cox proportional hazards model will be used to obtain the hazard ratio and 95% confidence intervals. The Cox proportional hazards model may include covariates such as baseline disease duration since symptom onset, baseline plasma NfL, and riluzole or edravone use (as specified in Section 5.6.1 under Covariates). P-value from the log rank test of the survival function will be provided. Hazard ratio (and corresponding 95% CI) comparing the treatment group will be obtained from Cox proportional hazard model. The log-rank test may be stratified by median baseline plasma NfL.

Whether a participant has had a permanent ventilation event, defined as (≥ 22 hours of mechanical ventilation [invasive or noninvasive] per day for ≥ 21 consecutive days), will be calculated using participant- and site-reported ventilation data from a weekly participant e-diary and from the eCRF, respectively. These data provide a yes/no answer as to whether a participant has used mechanical ventilation for ≥ 22 hours on each date (s)he has participated in the study. A participant will have reached the event of permanent ventilation if there is a “yes” answer on 21 or more consecutive days. The event will be defined as the first day of the ≥ 21 consecutive days with a “yes” answer. If there are dates in which there are discrepancies between the participant’s e-diary answer and the site’s eCRF answer, the eCRF data will supercede the e-diary data.

Due to the delay in the eCOA vendor, there are participants in Cohorts D1/D2 who did not have the ventilation e-diary at Day 1. To impute the ventilation event from these participants’ Day 1 and their first date e-diary, two approaches will be used. The primary analysis will utilize the participants’ closest ALSFRS-R Q12 answer available for respiratory insufficiency after their ediary initiation. If the participant responded 2 (continuous use of Bipap during the night), 3 (intermittent use of Bipap), or 4 (None), the mechanical ventilation use ≥ 22 hours for the dates between the date the participant’s ALSFRS-R questionnaire date and its prior

CONFIDENTIAL

The information contained herein may not be used, disclosed, or published without the written consent of Biogen MA Inc.

questionnaire date will be imputed as “no”. If the participant responded 1 (continuous use of Bipap during the night and day), the mechanical ventilation use ≥ 22 hours for the dates between the date of the participant’s ALSFRS-R questionnaire date and its prior questionnaire date will be imputed as “yes”. If the participant responded 0 (invasive mechanical ventilation by intubation or tracheostomy), the mechanical ventilation use ≥ 22 hours for the dates between the date of the participant’s ALSFRS-R questionnaire date and its prior questionnaire date will be imputed as “unknown”. Another approach is to impute the ventilation event for these gap dates as “yes” on trailing ventilation events since participants’ first ediary date, i.e., imputing “yes” for all missing e-diary dates if the first available e-diary entry after the missing dates is “yes”. If the second approach gives different imputation for any of the gap dates, a sensitivity analysis will be performed.

For dates with answers of “unknown” and missing gaps in the final data, available ALSFRS-R Q12 for respiratory insufficiency within 30 days window will be utilized in the same way as mentioned above to impute the ventilation status. Ventilation status will be imputed as “no” unless evidence of ventilation support from any source of data. For analysis of integrated data from Part 1 and Part 2, analyses will be conducted to compare Early-start BIIB105 120 mg versus Placebo/Delayed-start BIIB105 120 mg groups.

The subgroup analyses will be conducted by median baseline plasma NfL level.

Time to event since ALS symptom onset analyses might be performed post hoc if needed.

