A subject's *Suicidal Ideation Score* is defined as the maximal suicidal ideation question number (maximal of 1-5) with an answer "Yes" per visit. The score is defined as 0 if the subject answered "No" to all 5 Suicidal Ideation questions at that visit. A subject is considered to have treatment-emergent suicidal ideation if the subject had either new or worsening suicidal ideation. A subject is considered to have new suicidal ideation if the subject's Suicidal Ideation Score increased at postbaseline visit compared to a score 0 at baseline. A subject is considered to have worsening suicidal ideation if the subject's Suicidal Ideation Score increased at postbaseline visit compared to a positive score at baseline.

A subject is considered to have treatment-emergent suicidal behavior if the subject answered "Yes" to any suicidal behavior questions at any postbaseline visit while answered "No" to all suicidal behavior questions at baseline.

CONFIDENTIAL

The information contained herein may not be used, disclosed, or published without the written consent of
Biogen MA Inc.

CONFIDENTIAL

The information contained herein may not be used, disclosed, or published without the written consent of
Biogen MA Inc.

STATISTICAL ANALYSIS PLAN

Version No.: Final 1.0

Date: 05 September 2024

Author<s>: [REDACTED]

Study Title: A Phase 1/2 Multiple Ascending Dose Study With a Long-Term Open-Label Extension to Assess the Safety, Tolerability, Pharmacokinetics, Pharmacodynamics, and Effect on Disease Progression of BIIB105 Administered Intrathecally to Adults With Amyotrophic Lateral Sclerosis With or Without PolyCAG Expansion in the *ATXN2* Gene

Name of Study Treatment: BIIB105

Protocol No.: 275AS01 (Part 2 Final, Integrated Parts 1 and 2)

Study Phase: 1/2

Confidential Information

The information contained in this Statistical Analysis Plan (SAP) is confidential and may not be reproduced or otherwise disseminated without the approval of Biogen, Inc.

APPROVAL

This document has been reviewed and approved by:

		
SMT Statistician	Signature	Date
		
 , Biostatistics	Signature	Date
		
Medical Director, 	Signature	Date
		

VERSION HISTORY

SAP Version	Date	Primary Reasons for Amendment
1.0	September 05 2024	Not Applicable

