Part 2 is an open-label extension study to assess the long-term safety, tolerability, pharmacokinetics, pharmacodynamics, and effects on disease progression of BIIB105 administered IT to adults with ALS and polyQ-ALS who complete Part 1 through Week 25.

The purpose of this final Statistical Analysis Plan (SAP) is to describe in detail the planned statistical analyses on final data from Part 2 and selected integrated data from 275AS101 Part 1 and Part 2 as of the final database lock to support the final clinical study report (CSR).

The study was terminated early by the sponsor based on the results from study 275AS101 Part 1 and integrated interim results from Part 1 and Part 2 which indicated there was no effect in neurofilament and no clinical benefit in patients treated with BIIB105. The statistical analyses are being simplified for an abbreviated CSR due to the early termination of the study.

2. Study Overview

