4.1. Interim Analysis

An interim analysis of unblinded key safety, secondary, [REDACTED] endpoints (including PK, PD, clinical function) for Part 2 and integrated analyses of Part 1 and Part 2 was conducted following the completion of Day 175/176 visit for all Part 1 subjects to inform decisions on the BIIB105 clinical development program, the database lock date was April 29, 2024.

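### The final-lock survival analysis still lists the past interim cut (12 March 2024) as a censoring date, with no rule for when it applies

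*SAP*

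**What the plan says.** The Part 2/Integrated SAP, Section 5.6.5, gives the censoring rule in one sentence. Its first limb reads: "Participants without an event will be censored at the last known alive dates, defined as the interim cut date for 275AS101 (March 12, 2024"). The second limb, which completes the sentence, is "or as the last date in the database with any actual study visit or measurements indicating their alive status". The two dates are joined only by an 'or'. There is no condition, order of preference, or earlier-of or later-of rule. The section puts no 12 March limit on events.

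The same SAP describes its data differently. Its title page reads "Date: 05 September 2024". Section 1 says that it covers "final data from Part 2 and selected integrated data from 275AS101 Part 1 and Part 2 as of the final database lock", and Section 5.6.5 itself later refers to "missing gaps in the final data". Section 4.1 reports the interim analysis as already done: "the database lock date was April 29, 2024". Section 1 also records how the trial ended: "terminated early by the sponsor based on the results from study 275AS101 Part 1 and integrated interim results from Part 1 and Part 2".

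The required outputs include Kaplan-Meier medians, percentiles and the "proportion of participants with an event at a list of time points (Week 26, 52, 78, etc".), plus a log-rank test and a Cox hazard ratio. Section 6 states that vital status after withdrawal will not be collected for this analysis, and its list of changes does not mention the censoring date.

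**The concern.** A cut date from a completed interim analysis sits in a plan for the final lock, as an equal alternative to the last documented alive date. An event-free participant seen after 12 March has two admissible censoring dates, so two programmers working from the same sentence could report different medians and Week 52 or Week 78 proportions. Time to death, and time to death or permanent ventilation, are secondary endpoints of the integrated analysis (Protocol Section 4) and key endpoints in Section 2.1 of this SAP. What is at stake is whether those estimates are reproducibly specified and, under one way of applying the date, whether they are biased.

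**Working it through.** **1. Did follow-up pass 12 March 2024?** The interim database was locked on 29 April 2024. From 12 March, 19 days remain in March and 29 follow in April: 19 + 29 = 48 days. Termination rested on the interim results, so the study was still open at that lock. From 12 March to the SAP date of 5 September is 177 days. The documents give no final cut-off date.

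**2. What each reading does.** The Kaplan-Meier estimate is S(t) = product over event times of (1 - d/n), where d is the number of events and n the number at risk.

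- *Last documented alive date for everyone.* Events and event-free time run to the same point. There is no bias, and 12 March is never used.
- *12 March for both events and censoring.* This is coherent and essentially unbiased, but events and follow-up after 12 March are lost, contrary to Section 1.
- *12 March for censoring only, events counted to the final lock.* There are two opposite errors. Error 1: a participant followed beyond 12 March keeps a later death in d but loses later event-free time from n, so S(t) is too low. Error 2: a participant who left before 12 March stays in n up to that date without evidence of being alive, so S(t) is too high.

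**3. Size of the censoring-only reading.** The plan states no event count or power for survival, so there is no figure to reproduce. The illustration used the planned D1 and D2 numbers (Protocol Section 5.3.1): 36 + 12 = 48 active, 12 + 6 = 18 placebo, 66 in all.

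Entry dates were bounded as follows:

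- The 28 D1 participants added by Protocol Version 4.0 (9 September 2022) entered at most 550 days before 12 March 2024.
- Everyone entered at least 124 days before it. Day 176 less the 3-day window is Day 173, or 172 days after Day 1, and was reached by 29 April: 172 - 48 = 124.
- The other 66 - 28 = 38 entered at most 845 days before it, assuming no D1 or D2 dosing before Version 3.0 (18 November 2021). They were either spread over 124 to 845 days or all placed at 550 to 845 days.

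Assumed, not in the documents: event hazard 0.20 or 0.35 per year; withdrawal 0.15 or 0.30 per year, equal by arm; hazard ratio 1.0 or 0.7; uniform accrual; gap from the cut to the end of follow-up of 14, 48 or 177 days. That makes 2 x 3 x 2 x 2 x 2 = 48 scenarios, with 4,000 trials each.

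Change in Week 78 survival, in percentage points, against correct censoring:

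| Rule | Gap | Change |
|---|---|---|
| Error 1 alone | 14 days | -0.2 to -1.1 |
| Error 1 alone | 48 days | -0.8 to -3.5 |
| Error 1 alone | 177 days | -2.5 to -9.8 |
| Error 2 alone | all | +1.4 to +7.2 |
| 12 March for every event-free participant | all | -5.0 to +7.0 |

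At Week 52, error 1 gives -0.1 to -4.0 and error 2 gives +0.8 to +3.8. The mean number of events after 12 March is 0.2-0.5, 0.7-1.7 and 2.3-5.8 for the three gaps. The mean hazard ratio moves by at most 0.03, against a standard deviation of the log hazard ratio of 0.45 to 0.74.

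**4. Check of the consistent-cut reading.** A simpler simulation used 66 participants, no withdrawal, entry 26 to 110 weeks before the cut, a 177-day gap and 1,500 runs. Week 78 survival was:

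| Assumed median survival | True | Final cut | 12 March for events and censoring | 12 March for censoring only |
|---|---|---|---|---|
| 104 weeks | 0.595 | 0.593 | 0.592 | 0.527 |
| 156 weeks | 0.707 | 0.708 | 0.708 | 0.653 |

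The consistent cut costs about 5 to 7 later events, not bias. Censoring only is low by 0.593 - 0.527 = 0.066 and 0.708 - 0.653 = 0.055.

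**The case against.** The strongest reply is that the sentence carries its own answer. It censors at the last known alive date. Someone seen after 12 March has a later such date, and someone last seen before 12 March was not known to be alive on it. Either error requires a programmer to override the term being defined. That stands: the defect is a stale clause beside a usable rule, not a missing or wrong rule. It does not justify keeping the clause, which is listed first and has no function under the sensible reading.

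It is also fair that the larger figures are fragile. Error 1 and error 2 taken separately each apply 12 March to only part of the event-free group, a split that the SAP does not state. The 177-day gap treats the SAP date as the end of follow-up, which no section says. Only the 48-day gap is anchored in the documents, and even that borrows a lock date as the end of follow-up.

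A reader might infer that an alive date is the wrong censoring point for the ventilation composites, because being alive does not show ventilation status. The documents do not support that as a gap. Section 5.6.5 fills unknown dates and gaps from ALSFRS-R item 12 within a 30-day window and otherwise sets status to 'no' unless any source shows ventilation support. Censoring at last known ventilation status, with no rule for later deaths, could also recreate error 1.

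**Conclusion.** The point holds as an unresolved choice containing an outdated date. The text defect is certain; its effect on the reported results is not. With the last documented alive date there is no bias. With 12 March for both events and censoring there is a loss of later data but essentially no bias. Only censoring-only use biases the survival estimates: by about -0.8 to -3.5 points at Week 78 for error 1 with a 48-day gap, more only if follow-up ran much longer. If the date is applied to every event-free participant, the net sign is not fixed; the negative values come with the longest gap. These sizes rest on the assumed hazards, withdrawal and accrual. The real size cannot be computed, because the final cut-off, later events and withdrawals are not given.

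A reader might infer that the survival results are biased or the treatment comparison compromised. The documents support neither. They do not show that the date was applied, and the hazard ratio is essentially unchanged when withdrawal is equal by arm. The study had also already been stopped on interim results, and this SAP supports an abbreviated report. The correction is worth making so that required secondary estimates have one definition.

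**What to change.** In Section 5.6.5 of the Part 2/Integrated SAP, delete the 12 March 2024 date. State one final data cut-off that applies to both events and censoring. Censor event-free participants at the earlier of that cut-off and the last date with documented alive status. Leave the ventilation rule as it is. The cost is one or two sentences of SAP text and a small programming change, with no new data.

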5.6.6. Subgroup Analyses for Efficacy Endpoints

- As no notable differences were observed in the interim analyses, no subgroup analyses are planned.

5.7. Safety Endpoints

The safety population will be used for the analyses of the safety data. Safety data will be summarized using descriptive statistics by dose level and/or cohort.

Adverse events (AEs) and serious adverse events (SAEs), and CSF laboratory data, will be evaluated for safety. Safety data will be summarized using descriptive statistics.

For analyses of Part 2, safety data will be summarized by their initial dose level in Part 2 (BIIB105 60 mg vs BIIB105 120 mg), with baseline defined as the first dose of BIIB105 60 mg or BIIB105 120 mg in Part 2. [REDACTED]

[REDACTED] For participants who escalate from 60 mg to 120 mg in Part 2, AEs and CSF laboratory data since their first dose escalation to 120 mg will be summarized separately.

For integrated analyses of Part 1 and Part 2 for Cohorts D1 and D2, selected safety data from the BIIB105-treated periods in Part 1 and Part 2 will be summarized, with baseline defined as the first dose of 120 mg BIIB105, regardless of whether the participant started this dose in

CONFIDENTIAL

The information contained herein may not be used, disclosed, or published without the written consent of Biogen MA Inc.

Part 1 or Part 2. [REDACTED]

To assess the overall safety profile of 60 mg BIIB105, integrated Part 1 and 2 safety data may be presented for any participant who received at least one dose of 60 mg BIIB105, with baseline defined as first dose of 60 mg BIIB105. As participants on the 60 mg dose in Part 2 was increased to 120 mg starting December 2023, data since their first dose of escalation to 120 mg will not be included in the analysis for 60 mg BIIB105. To assess the overall safety profile of 120 mg BIIB105, integrated Part 1 and 2 safety data may be presented for any participant who received at least one dose of 120 mg BIIB105, with baseline defined as the first dose of 120 mg BIIB105, which also includes participants escalate from 60 mg to 120 mg in Part 2.

Table 4. Pooled Groups for Safety Endpoints.

Pooled Group	Pool BIIB105 120 mg DL	Pool BIIB105 60 mg	Pool BIIB105 120 mg
Treated Periods	BIIB105 120 mg treated period	BIIB105 60 mg treated period	BIIB105 120 mg treated period
Participants Included	Total of all participants in Part 1 Cohorts D1 and D2 exposed to BIIB105 120 mg during either Part 1 (i.e. DL1) or initiated during Part 2 (DL2); regardless of whether they entered Part 2. Note a subset of tables will be presented for DL1 and DL2.	All participants who received at least one dose of BIIB105 60 mg in either Part 1 or Part 2.	All participants who received at least one dose of BIIB105 120 mg in either Part 1 or Part 2.
Data Included	All data from BIIB105 120 mg during Part 1 and Part 2. For those who initiated BIIB105 120 mg in Part 2, data from Part 1 are not included here	All data since first dose of BIIB105 60 mg, and before their first dose of escalation to 120 mg in Part 2.	All data since first dose of BIIB105 120 mg.

CONFIDENTIAL

The information contained herein may not be used, disclosed, or published without the written consent of Biogen MA Inc.

Table 5: Analysis Methods for Part 2 and Integrated Summary of Safety Data

Endpoints	Summary/Analyses	Part 2		Integrated Part 1 and Part 2		
		60 mg	120 mg	Pool BIIB105 120 mg DL (DL1, DL2)	Pool BIIB10 5 60 mg	Pool BIIB105 120 mg
Disposition	Accounting of participants	x	x	x		
Medical history	Summary	x	x			
Concomitant medications	Summary	x	x			
Adverse event	Overall summary AE by SOC and PT SAE by SOC and PT Adjusted incidence rate	x	x	x	x	x
CSF lab tests	Shift table Spaghetti plots Post-baseline evaluation of CSF WBC and CSF protein	x	x	x	x	x
Other lab tests	Descriptive analysis, shift table	x	x			
Vital Signs	Descriptive analysis	x	x			
ECG	Descriptive analysis, shift table	x	x			
Neurological Examination	Descriptive analysis	x	x			
PK	CSF concentration descriptive statistics	x		x		

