13.3. Methods of Analysis

13.3.1. Safety

For analyses of Part 1, safety data will be summarized by dose level and treatment assignment in Part 1 (BIIB105 5 mg [Cohort A], 20 mg [Cohort B], 60 mg [Cohorts C1+ C2], 120 mg [Cohorts D1+D2], Pooled Placebo 1+2), as well as by cohort and treatment assignment in Part 1 (BIIB105-treated Cohorts A, B, C1, C2, D1, and D2; Pooled Placebo 1 and Pooled Placebo 2).

For analyses of Part 2, safety data will be summarized by dose level in Part 2 (BIIB105 60 mg vs BIIB105 120 mg).

For integrated analyses of Part 1 and Part 2 for Cohorts D1 and D2, safety data from the BIIB105-treated periods in Part 1 and Part 2 will be summarized, with baseline defined as the first dose of 120 mg BIIB105, regardless of whether the participant started this dose in Part 1 or Part 2.

To assess the overall safety profile of 60 mg BIIB105, integrated Part 1 and 2 safety data may be presented for any participant who received at least one dose of 60 mg BIIB105, with baseline defined as first dose of 60 mg BIIB105. To assess the overall safety profile of 120mg BIIB105, integrated Part 1 and 2 safety data may be presented for any participant who received at least one dose of 120 mg BIIB105, with baseline defined as the first dose of 120 mg BIIB105.

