2.2. Study Design

Part 1

Part 1 is a Phase 1/2, randomized, double-blind, placebo-controlled, MAD evaluation of the safety, tolerability, and PK of BIIB105, administered IT to approximately 98 participants (76 participants with ALS and 22 participants with polyQ-ALS) at approximately 15 sites globally. Cohorts A, B, C1, and C2 will receive up to 5 doses over approximately 3 months. Cohorts D1 and D2 will receive up to 8 doses over approximately 6 months.

Adult participants with ALS will be randomized at a ratio of 3:1 (active drug:placebo) in Cohorts A, B, C1, and D1. Adult participants with polyQ-ALS will be randomized at a ratio of 3:1 in Cohort C2 and at a ratio of 2:1 in Cohort D2. Cohorts C1 and C2 can dose concurrently. Cohorts D1 and D2 can dose concurrently.

Participants in Cohorts D1 and D2 who enroll in Part 2 will not complete the Follow-up Visits and TCs in Part 1 that occur after Day 175; they will enroll into Part 2 and follow the Part 2 visit schedule.

Part 2

Part 2 is an open-label evaluation of BIIB105 administered IT to participants with ALS and polyQ ALS who have completed Part 1 through Week 25 (Day 175 Visit for Cohorts A, B, C1, C2; Day 176 Visit for Cohorts D1, D2).

Participants will receive up to approximately 41 doses in Part 2. Two dose levels will be administered – participants from Part 1 Cohorts A, B, C1, and C2 will receive 60 mg BIIB105; participants from Part 1 Cohorts D1 and D2 will receive 120 mg BIIB105.

[figure not shown]
In Part 2, the 60 mg dose may be increased, at the Sponsor's discretion, to doses up to 120 mg. Before increasing the dose level, the SST must review safety and PK data for Cohort D1 and D2 (Part 1) and there must be agreement that the current emerging safety, tolerability, and PK data support the dose increase. The 60 mg dose in Part 2 was increased to 120 mg following the SST review on 13 December 2023.

Doses in Part 2 may also be decreased at the Sponsor's discretion at any time during the study.

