The actual scores and changes from baseline in each measure will be summarized using descriptive statistics. Missing data will be imputed using multiple imputation. Multiple imputation will be performed on actual values, domains, total scores, or summary scores depending on the endpoint. In addition, each clinical function measure will be analyzed using an ANCOVA model. The model may include covariates such as corresponding baseline value, baseline NfL, duration from onset of symptoms to the first dose of study treatment, broad ALS/polyQ ALS, and riluzole or edaravone use. The model will be used to estimate least-square (LS) means for each treatment group with standard errors (SEs), and LS mean differences between treatment groups with corresponding 95% confidence intervals (CIs). The p-values comparing treatment differences will also be presented. LS mean changes over time will be also presented in line plots.

For integrated analyses of Part 1 and Part 2 for Cohorts D1 and D2, treatment groups will be defined as Early-start BIIB105 120 mg (i.e., those who initiated BIIB105 120 mg in Part 1) and Placebo/Delayed-start BIIB105 120 mg (i.e., those who received placebo in Part 1), with baseline defined as Part 1 baseline. Clinical function data will be presented by treatment group (Early-Start BIIB105 120 mg vs Placebo/Delayed-start BIIB105 120 mg). They might also be presented by cohort and treatment group as a sensitivity analysis (Cohort D1 Early-start vs Placebo/Delayed-start; Cohort D2 Early-start vs. Placebo/Delayed-start).

CONFIDENTIAL

The information contained herein may not be used, disclosed, or published without the written consent of
Biogen MA Inc.

Due to the washout period between Part 1 and Part 2 for all participants in Cohorts A, B, C1, and C2, Part 2 clinical function data for these cohorts will be presented separately from Part 1. Descriptive summaries will be presented for the combined cohort (A+B+C1+C2) by their initial dose level, i.e. 60 mg in Part 2 with baseline defined as Part 2 baseline. As participants on the 60 mg dose in Part 2 were increased to 120 mg starting December 2023, visits since first dose escalation to 120 mg will not be included in the analysis for Part 2 BIIB105 60 mg.

CONFIDENTIAL

The information contained herein may not be used, disclosed, or published without the written consent of
Biogen MA Inc.

Table 3: Analysis Methods for Part 2 and Integrated Summary of Efficacy and PD Data

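### At the Part 2 escalation from 60 mg to 120 mg, final SAP 5.7 visibly separates only AEs and CSF laboratory data, so other safety findings first seen on 120 mg are summarised under 60 mg

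*SAP*

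**What the plan says.** Section 2.2 of the final SAP records that the escalation took place: "The 60 mg dose in Part 2 was increased to 120 mg following the SST review on 13 December 2023". Participants from Cohorts A, B, C1 and C2 start Part 2 on 60 mg; those from D1 and D2 start on 120 mg.

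For Part 2, section 5.7 says "safety data will be summarized by their initial dose level in Part 2 (BIIB105 60 mg vs BIIB105 120 mg"). Protocol 13.3.1 has no word for initial: "safety data will be summarized by dose level in Part 2 (BIIB105 60 mg vs BIIB105 120 mg"). For participants who escalate, 5.7 adds that "AEs and CSF laboratory data since their first dose escalation to 120 mg will be summarized separately".

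A later paragraph of 5.7, on the integrated 60 mg safety profile, says that "data since their first dose of escalation to 120 mg will not be included in the analysis for 60 mg BIIB105". Table 4 repeats this for the integrated 60 mg pool. For clinical function, 5.6.1 says that "visits since first dose escalation to 120 mg will not be included in the analysis for Part 2 BIIB105 60 mg".

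Table 5 lists the planned safety summaries. Other laboratory tests and ECG (each entered as "Descriptive analysis, shift table"), vital signs and neurological examination are marked under Part 2 60 mg and Part 2 120 mg, and under none of the integrated pools.

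**The concern.** The column headed 60 mg holds participants who were later dosed at 120 mg. If their data are not cut or split at the switch, findings that arise on 120 mg are reported as 60 mg findings, and the 120 mg column omits those participants altogether.

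The stated objective of this analysis is long-term safety and tolerability. The protocol's benefit-risk section names metabolic and blood-pressure effects as possible consequences of lowering ATXN2. Those would show in chemistry, weight and vital signs, which are among the domains with no visible cut. Table 5 labels the column by dose alone, so a reader of the output could not tell that it mixes two doses.

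**Working it through.** **1. The rule for each type of Part 2 data at escalation (final SAP, visible text)**

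| Data | Rule at first 120 mg dose | Section | In an integrated 120 mg pool? |
|---|---|---|---|
| Protocol deviations | Summarised separately | 5.4 | Not applicable |
| Concomitant treatments | Summarised separately | 5.5 | No |
| Clinical function, Part 2 60 mg | Later visits excluded | 5.6.1 | Not applicable |
| AEs and SAEs | Summarised separately | 5.7 | Yes |
| CSF laboratory data | Summarised separately | 5.7 | Yes |
| Other laboratory tests | None stated | 5.7.2 | No |
| Vital signs and weight | None stated | 5.7.3 | No |
| ECG | None stated | 5.7.4 | No |
| Neurological examination | None stated | 5.7.5 | No |

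The domain sections widen the data included. Shift analyses in 5.7.2 take every visit with a result. Section 5.7.4 uses all post-baseline ECG data to identify abnormalities. Section 5.7.3 counts post-baseline vital-sign and weight abnormalities with no limit by dose. None of them mentions escalation. Where the SAP wants a split or a cut elsewhere, it writes one.

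**2. How many participants**

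Planned cohort sizes from protocol 5.3.1: A 6+2, B 6+2, C1 9+3, C2 3+1. So 8 + 8 + 12 + 4 = 32 of the 98 planned. This is a ceiling. Entry to Part 2 normally requires completing Week 25 of Part 1, and only those still on 60 mg in December 2023 could escalate. The documents give neither number.

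**3. How long**

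Days from 13 December 2023 to three dates in the SAP, and the same in four-week dosing intervals:
- 12 March 2024 (interim cut, 5.6.5): 90 days; 90/28 = 3.2
- 29 April 2024 (interim database lock, 4.1): 138 days; 138/28 = 4.9
- 5 September 2024 (SAP date): 267 days; 267/28 = 9.5

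That is about 3 to 9 complete intervals per participant, if each switched at once and stayed on treatment. Weight, HbA1c and lipids are 12-weekly in maintenance (protocol Table 3), so for these the range is about 90/84 = 1.1 to 267/84 = 3.2 assessments. Actual switch dates and last-dose dates are not given.

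**4. What this can do to an ever-abnormal count (illustration; all rates assumed)**

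Assume 13 visits on 60 mg, independent visits, and a 2% chance of an abnormal value at each. The proportion ever abnormal is 1 − 0.98^13 = 23.1%. Now leave m visits on 120 mg in the same column, with a per-visit rate p of 2% (no dose effect) or 4%, using 1 − 0.98^13 × (1 − p)^m:
- m = 3: 27.6% (p = 2%), 32.0% (p = 4%)
- m = 9: 35.9% (p = 2%), 46.7% (p = 4%)

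The count rises even with no dose effect, because follow-up is longer. It rises further if 120 mg carries more risk.

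**5. Protocol against SAP**

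Section 6 of the final SAP lists two changes from the protocol, both about time-to-event endpoints. The move from dose level to initial dose level is not among them.

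**The case against.** **Redaction.** Text is blacked out in 5.7 between the grouping sentence and the escalation sentence, which is where a general rule could sit. Redacted text cannot be counted as missing. This stands, and it limits confidence. Nothing visible in Table 5 or in 5.7.2 to 5.7.5 points to such a rule.

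**A visible sentence may already cover it.** The sentence excluding post-escalation data from the 60 mg analysis could be read as general. Its paragraph concerns the integrated 60 mg profile, and Table 4 ties the same rule to that pool. The four domains are in no pool, so the rule does not reach them.

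**The scope is deliberate.** Section 5.7 opens by naming AEs, SAEs and CSF laboratory data as what will be evaluated, the report is abbreviated, and the endpoint is AE and SAE incidence. This stands as to weight: the affected tables are secondary and descriptive. The plan nevertheless still produces them.

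**The findings are not lost.** A reader might infer that a finding on 120 mg disappears from every 120 mg output. The documents do not support that. Under protocol 12.1.1, an abnormal result that the investigator considers clinically significant, or that needs corrective therapy, is an AE, and AEs after the first 120 mg dose enter the integrated 120 mg pool. All four domains are also listed by participant. What is missing is a 120 mg summary of threshold crossings and shifts that were not AEs.

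**Initial dose level may just make the protocol workable.** Protocol 13.3.1 does not say how to classify someone whose dose changes. That is a fair reading, so the point about Section 6 is one of documentation.

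**Conclusion.** The concern holds on the visible text. For other laboratory tests, vital signs and weight, ECG and neurological examination, post-escalation data are summarised under 60 mg, and findings that are not AEs appear in no 120 mg summary. This is a should-fix at medium confidence, because of the redaction and the secondary role of these tables.

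The size is not known. At most 32 planned participants are affected, over 90 to 267 days from 13 December 2023. The upper end assumes immediate switching and treatment up to the SAP date, which no document confirms.

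A reader might go further and infer that the 60 mg against 120 mg comparison is biased toward no difference. The documents do not show that. No inferential safety comparison is planned, the two Part 2 groups come from cohorts not randomised against each other, and the direction depends on the true rates. If risk rises with dose, the mixing narrows the visible gap; if it does not, the longer follow-up alone makes 60 mg look worse.

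**What to change.** Four changes to the final SAP:

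1. In 5.7, extend the escalation sentence from AEs and CSF laboratory data to every safety domain in Table 5.
2. State that all Part 2 60 mg summaries, both counts and person-time, end at the participant's first 120 mg dose, as 5.6.1 and the integrated 60 mg pool already do. This also settles the AE tables: separate summary of post-escalation AEs does not by itself say that they leave the Part 2 60 mg column.
3. Show later data in a separate column for participants escalated from 60 to 120 mg, and state its baseline. Baseline at the first 120 mg dose isolates change on 120 mg but hides change accrued since Part 2 entry; the SAP should choose and say why.
4. Note in Section 6 that the protocol's dose level in Part 2 was implemented as initial dose level.

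If the redacted text already contains the rule, a cross-reference in 5.7.2 to 5.7.5 and a footnote to Table 5 would be enough.

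The cost is SAP wording and a date cut of a kind the SAP already specifies elsewhere. No new data are needed. The downside is shorter follow-up in the 60 mg column.
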